### **Anthropometric cohort**

The cohort will include all infants who meet the following criteria:

- Selected to be in the anthropometric cohort
- Included in the primary analysis cohort
- Alive and participating in the study at day 28

## **6.3 Covariates and Subgroups**

(ICH E3; 9.7.1, 11.4.2.1. ICH E9; 5.7)

### **Subgroups**

Exploratory analyses in which the data are stratified by country will be done for all outcomes analysed in the Primary cohort. In addition, the primary outcome will be analysed in the following subgroups:

- Deliveries >2 hours after administration of the study pills
- Deliveries  $\leq 2$  hours after administration of the study pills
- Deliveries in the wet season (June–October)
- Deliveries in the dry season (November–May)
- Overweight and obese mothers ( $BMI \geq 25.0 \text{ kg/m}^2$ )
- Normal weight and underweight mothers ( $BMI < 25.0 \text{ kg/m}^2$ )
- Newborns delivered via caesarean
- Vaginal deliveries

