## 5 Sample Size

(ICH E3; 9.7.2. ICH E9; 3.5)

The study was originally designed to assess the effect of the intervention on mortality. We assumed mortality in the placebo arm would be at least 1.4% and that the intervention would reduce mortality by 40%. Based on these parameter values, and allowing for 8% loss to follow-up, it was estimated that a total of 12,500 women would need to be recruited to achieve 80% power to detect such an effect.

However, during the course of the study data from the MORDOR study was published (Keenan et al., 2018) which suggested that the intervention was unlikely to achieve a 40% reduction. Study power was also negatively impacted by the lower than anticipated incidence of mortality (the observed mortality up to Jan 2020 was lower than anticipated (0.7%) probably because of the improved care associated with participating in the trial), and by the recruitment freeze between March and August 2020, which resulted in the target sample size being reduced from 12,500 to 12,000.

Because of this loss of study power, we decided to change the primary outcome from neonatal mortality to the composite endpoint of neonatal mortality + neonatal Sepsis. The revised power calculations are shown in Table 6. The calculations are based on mortality and sepsis data collected up to the end of Jan 2020 and effect size of 25% (RR=0.75) for mortality and 30% (RR=0.70) for sepsis. The revised study power is 82% power.

**Table 6** Revised study power calculation

Gambia parameters		Gambia	Control	AZI	Power
Total N	7000	N	3500	3500	
Incidence sepsis	1.9%	Sepsis	2.2%	1.6%	0.54
Incidence mortality	0.7%	Mortality	0.8%	0.6%	0.17
Proportion deaths due to sepsis	31%	Combined	2.8%	2.0%	0.60

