### **Burkina Faso parameters**

### **Burkina Faso**

Total N	5000	N	2500	2500	
Incidence sepsis	1.8%	Sepsis	2.1%	1.5%	0.39
Incidence mortality	0.7%	Mortality	0.8%	0.6%	0.13
Proportion deaths due to sepsis	17%	Combined	2.8%	2.0%	0.46
RR sepsis	0.7	Overall			
RR mortality	0.75	N	6000	6000	
		Sepsis	2.2%	1.5%	0.76
Significance level (z-value)	1.96	Mortality	0.8%	0.6%	0.26
		Combined	2.8%	2.0%	0.82

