## 6.6 Accounting for differences between countries

(ICH E3; 9.7.1, 11.4.2.4. ICH E9; 3.2)

The regression models used to analyse outcomes in the Primary and Anthropometric cohorts will include country. Hence these analyses will be adjusted for country (in addition to 1-minute Apgar score and birthweight). In the analysis of the Primary cohort, we will do separate analyses in each country using a Wald test to test the treatment x country interaction. This analysis will be considered to be exploratory. No adjustment for country will be made in the analysis of the Carriage cohort because of the smaller size of this cohort.

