## 8 Efficacy Analyses

### 8.1 Primary analysis cohort

#### Primary outcome

We will report the proportion that meet the criteria for the primary outcome (death or sepsis within 28 days of birth) in each arm.

The null hypothesis of no difference between the arms will be tested by fitting a logistic regression model that, in addition to study arm, includes 1-minute Apgar score and birthweight as continuous, linear covariates. The p-value, odds ratio and

confidence interval associated with study arm will be reported, with the confidence interval and p-value being based on a Wald test.

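### The SAP splits the primary outcome by four factors besides country but plans no test of whether the treatment effect differs by any of them

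*SAP*

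**What the plan says.** Under Subgroups, SAP Section 6.3 first sets out the country analyses: "Exploratory analyses in which the data are stratified by country will be done for all outcomes analysed in the Primary cohort". It then continues that, in addition, "the primary outcome will be analysed in the following subgroups". The list gives deliveries more than 2 hours and up to 2 hours after the study pills, wet and dry season, maternal BMI at or above 25 and below 25, and caesarean and vaginal delivery.

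For country, Section 6.6 plans separate analyses "using a Wald test to test the treatment x country interaction", and adds: "This analysis will be considered to be exploratory". Sections 6.3 and 8.1 have no matching test for the other four factors. The primary model in Section 8.1 contains study arm and covariates, and reports the odds ratio, p-value and "confidence interval associated with study arm will be reported, with the confidence interval and p-value being based on a Wald test". It has no treatment-by-subgroup term, and the SAP states no rule for interpreting the eight subgroup results.

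**The concern.** A paired subgroup analysis asks one question: does the effect differ between the two halves? Two separate analyses give two odds ratios and two p-values. Each p-value tests whether the effect in that half is zero, and neither tests whether the halves differ. The SAP uses the right tool for country and leaves it out for the other four factors.

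At stake is how the subgroup results are read. A trial with about 80% power overall has much less in each half, so one significant and one non-significant half is a common outcome even when the effect is identical. With no interaction test planned, the reader has no better statistic to set against that pattern.

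**Working it through.** **Inputs (SAP Section 5, Table 6).** Sepsis 1.9% (The Gambia) and 1.8% (Burkina Faso); mortality 0.7% in both; share of deaths due to sepsis 31% and 17%; RR 0.70 for sepsis and 0.75 for mortality; 6000 per arm, split 7:5 by country; "Significance level (z-value") of 1.96.

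**Step 1: reproduce the stated power.** Control rate = 2 × incidence / (1 + RR); AZI rate = RR × control rate; combined = sepsis + (1 − share of deaths due to sepsis) × mortality.

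- The Gambia: control 2.235% + 0.69 × 0.8% = 2.787%; AZI 1.565% + 0.69 × 0.6% = 1.979%.
- Burkina Faso: control 2.118% + 0.83 × 0.8% = 2.782%; AZI 1.482% + 0.83 × 0.6% = 1.980%.
- Weighted 7:5: 2.785% against 1.979%.

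SE = √[(0.02785 × 0.97215 + 0.01979 × 0.98021) / 6000] = 0.002783. Expected z = 0.008055 / 0.002783 = 2.894. Power = Φ(2.894 − 1.96) = 0.825, against the stated 82%. All nine powers in Table 6 reproduce to within 0.01.

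**Step 2: same effect in both halves.** In a subgroup holding a fraction f of the cohort, the expected z is 2.894 × √f, so power = Φ(2.894√f − 1.96). With powers a and b in the two halves, P(exactly one p<0.05) = a(1 − b) + b(1 − a). The SAP gives no subgroup shares, so a range is assumed:

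| Split | Power, larger half | Power, smaller half | Exactly one significant |
|---|---|---|---|
| 50/50 | 0.53 | 0.53 | 0.50 |
| 60/40 | 0.61 | 0.45 | 0.51 |
| 70/30 | 0.68 | 0.35 | 0.55 |
| 80/20 | 0.74 | 0.25 | 0.62 |
| 90/10 | 0.78 | 0.15 | 0.70 |

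For example, at 70/30: 0.678 × 0.646 + 0.354 × 0.322 = 0.552.

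**Step 3: four pairs together.** 20,000 simulated trials with independent factors, unadjusted Wald tests and a uniform effect gave at least one discordant pair in 80% (all splits 50/50), 86% (all 70/30) and 90% (all 90/10).

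**Step 4: interaction tests instead.** In the same simulations, the interaction test flagged a difference in about 5% of trials per pair (2–5% where one half is very small), and at least one of four did so in about 16–19%. Independent tests would give 1 − 0.95⁴ = 18.5%.

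**Step 5: power of the interaction test.** Suppose the planned effect (OR 0.705, log OR 0.350 in size) holds in one half and is absent in the other, with 2.785% in both arms there. At 50/50 there are 3000 per arm per half, and the variance of the difference in log ORs is 3 / (3000 × 0.02785 × 0.97215) + 1 / (3000 × 0.01979 × 0.98021) = 0.0369 + 0.0172 = 0.0541. Then z = 0.350 / 0.2326 = 1.50 and power = Φ(1.50 − 1.96) = 0.32. The same formula gives 0.27–0.29 at 70/30 and 0.14–0.15 at 90/10, depending on which half holds the effect.

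**The case against.** **The analyses can be read as exploratory.** The Subgroups paragraph opens with that word, and nothing makes the eight subsets confirmatory. This stands and lowers the seriousness. But the label is attached to the country analyses, and those are exploratory and still get an interaction test.

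**The plan does not say that differences will be inferred from subgroup p-values.** This also stands. A reader might infer that the plan leads to a false subgroup claim in half or more of trials. The documents do not support that: 50–70% is the chance that the two halves fall on opposite sides of p=0.05, and it becomes an error only if someone compares verdicts. Odds ratios and intervals reported as in Section 8.1 would let a careful reader see overlap. They still would not supply the missing test.

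**Post-dose factors.** A reader might infer that both dose-to-delivery time and mode of delivery are unsound because they are settled after dosing. For mode of delivery the SAP answers this: Section 4.4 lists it among variables measured after randomisation but judged unlikely to be affected by the intervention. Dose-to-delivery time is not on that list, so a narrower remark stands: it is known only after dosing, and the SAP does not say whether treatment could alter it.

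**Interaction tests are weak.** True, as Step 5 shows. That limits what a non-significant result can mean, but it does not make separate p-values a valid comparison.

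**Importance.** Nothing in the SAP shows that any of these contrasts would steer implementation, so that is not claimed.

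**Conclusion.** The point holds as a gap in method. For dose-to-delivery time, season, maternal BMI and mode of delivery, the SAP plans separate analyses and gives no valid test of effect difference, although it specifies one for country.

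Under a uniform effect at the planned power, discordant significance within a pair has a probability of about 50% at an even split, rising to 70% at 10/90, against about 5% for an interaction test. These figures rest on the Table 6 rates, on assumed subgroup shares, and on equal event rates and effects in both halves. The joint figures also assume independent factors and unadjusted tests. Covariate adjustment would shift power slightly without changing the conclusion. The 70% figure needs a stratum of only about 29 events (12,000 × 0.10 × 2.38%).

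The primary estimate, its test and the trial's main conclusion are not affected.

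**What to change.** Extend the Wald interaction test of Section 6.6 to the four factors in Section 6.3:

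- For each pair, fit the primary logistic model in the whole cohort with a treatment-by-subgroup term.
- Report the interaction p-value beside the two subgroup odds ratios and confidence intervals.
- State that any claim of a subgroup difference rests on the interaction test and not on within-subgroup p-values.
- Label all four analyses exploratory.
- Note that dose-to-delivery time is known only after dosing and is not covered by the statement in Section 4.4.

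The cost is four model terms and a few sentences; no new data are needed and the primary analysis does not change. Two limits should be written in: with this low power, a non-significant interaction is not evidence of a uniform effect, and four unadjusted tests still carry about a 16–19% chance of at least one false positive.

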### **Covariate adjustment**

Where possible, regression models will be used to improve statistical power (Kahan, 2014). We will use linear regression for continuous outcomes and logistic regression for binary outcomes.

In the analysis of outcomes in the Primary and Anthropometric cohorts, the models will include country as a binary predictor, and 1-minute Apgar score and birthweight as continuous linear terms.

In the analysis of data from the Carriage cohort, logistic regression will be used to adjust for day 0 maternal carriage (day 0 neonatal carriage cannot be adjusted for because it is recorded after treatment).

No covariate adjustment will be used in the analysis of the aetiologies of sepsis (Primary cohort) because the prevalence of the outcomes in this analysis is anticipated to be low and logistic regression may be unreliable in this situation (Peduzzi et al., 1996).

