### Baseline variables

The following variables will be used to characterise the study population. The list includes variables that are measured post–randomisation and are therefore not, strictly speaking, baseline variables. We have chosen to include these variables in the list of baseline variables because they are unlikely to be affected by the intervention.

*Maternal Ethnicity:* Mandinka, Wollof, Fula, Jola, in The Gambia and Mossi, Gourounsi and Peulh in Burkina Faso.

*Maternal age:* median and interquartile range

*Apgar score (1–minute):* ≤3, 4–7, 8–10

*Birthweight (kg):* <1.5, 1.5–2.4, 2.5–3.9, 4.0+

*Sex of newborn:* male, female

*Mode of delivery:* vaginal, caesarean section (CS)

*Congenital malformation (visible):* yes, no

*Birth outcome:* live birth, fresh still birth, macerated still birth

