## 7 Summary of Study Data

See dummy tables and consort diagram.

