### **Secondary outcomes**

The secondary outcomes are all binary and will therefore be analysed using logistic regression as described for the primary outcome (except the specific aetiologies of sepsis which will be analysed using Fisher's exact test because these are rare outcomes).

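### The primary model is specified both with and without country, has no sensitivity model free of post-dose newborn covariates, and is extended to maternal and rare outcomes without the rules it needs

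*SAP*

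**What the plan says.** **Covariates.** SAP section 6.3 (Covariate adjustment) states that in the Primary and Anthropometric cohorts "the models will include country as a binary predictor, and 1-minute Apgar score and birthweight as continuous linear terms". Section 6.6 agrees: "The regression models used to analyse outcomes in the Primary and Anthropometric cohorts will include country". Section 8.1 (Primary outcome) describes a logistic model that, besides study arm, "includes 1-minute Apgar score and birthweight as continuous, linear covariates". It does not mention country.

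**Timing.** Women are dosed in labour (section 4.1), so both newborn measures follow dosing. Section 4.4 (Baseline variables) concedes that some listed variables are measured after randomisation and keeps them "because they are unlikely to be affected by the intervention". For the carriage cohort, section 6.3 says "day 0 neonatal carriage cannot be adjusted for because it is recorded after treatment". Section 8.2 (Infant carriage) gives the fuller reason: those samples may be affected by treatment.

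**Secondary outcomes.** Section 8.1 says: "The secondary outcomes are all binary and will therefore be analysed using logistic regression as described for the primary outcome". Only the aetiologies of sepsis are exempt and go to Fisher's exact test. Section 6.3 explains that exemption by expected low prevalence, where "logistic regression may be unreliable in this situation". In the carriage cohort, section 8.2 switches to an unadjusted odds ratio and Fisher's test below 4% prevalence, a cut-off justified as 10 events per parameter. Section 9 uses Fisher's test for hospitalisations and deaths as safety data.

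**The concern.** Four gaps follow from how this one model is written and reused.

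1. Two analysts could fit different primary models, one with country and one without, and each could point to the SAP.
2. If treatment changed the 1-minute Apgar score or birthweight, the adjusted odds ratio would leave out that part of the effect. No prespecified model without these covariates stands beside it.
3. Read literally, newborn Apgar and birthweight enter the models for all seven maternal outcomes in section 3.4. A mother of twins has two values of each, and no rule says which to use.
4. Secondary outcomes with few events would be given adjusted Wald results that the SAP itself treats as doubtful for rare outcomes. Neonatal hospitalisation, maternal hospitalisation and maternal death also have a second test in section 9, and the SAP does not say which result stands for the secondary endpoint.

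**Working it through.** **Primary model, passages side by side.** Section 6.3: arm, country, Apgar, birthweight (4 parameters, intercept not counted). Section 6.6: country included, in addition to Apgar and birthweight. Section 8.1: arm, Apgar, birthweight (3 parameters).

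**Post-dose covariates.** The SAP gives no treatment effect on Apgar and no prognostic strength for it, so neither a bias nor a change in power can be computed. Section 8.1 does report proportions by arm. At the rounded rates of Table 6, 0.028 × 6,000 = 168 and 0.020 × 6,000 = 120 events, so a reader could derive a crude OR of (120 × 5,832)/(168 × 5,880) = 0.71 (95% CI 0.56 to 0.90). That comparison is not adjusted for country and is not prespecified.

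**The SAP's sparse-data figure.** In the carriage cohort of 500, 4% gives 0.04 × 500 = 20 events. With two parameters (arm, day 0 carriage), 20/2 = 10 events per parameter, which matches the stated reason for the cut-off.

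**The same basis in the Primary cohort (12,000).**
- Section 8.1 model: 10 × 3 = 30 events; 30/12,000 = 0.25%.
- Model with country: 10 × 4 = 40 events; 40/12,000 = 0.33%.
- The literal 4% would be 0.04 × 12,000 = 480 events, more than the primary outcome is expected to yield.

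**Expected events** (incidences from Table 6, recruitment from section 4.1).
- Primary outcome: 168 + 120 = 288; 288/4 = 72 per parameter (288/3 = 96 without country).
- Sepsis: 0.019 × 6,750 + 0.018 × 5,250 = 128.25 + 94.5 = 222.75; 222.75/4 = 56.
- Mortality: 0.007 × 12,000 = 84; 84/4 = 21. The 0.7% is observed mortality; deaths left after the excluded causes could be fewer.
- Culture-confirmed sepsis: no rate is given. The share of sepsis cases needed is 30/222.75 = 13.5% (3 parameters) or 40/222.75 = 18.0% (4 parameters). Assumed shares of 5%, 10% and 20% give 11, 22 and 45 events.
- Country-specific analyses (3 parameters, 30 events): 30/128.25 = 23.4% in The Gambia and 30/94.5 = 31.7% in Burkina Faso.

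**Wald against Fisher** (hypothetical counts, 6,000 per arm, arm-only model).

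| Events | Wald p | Fisher p |
|---|---|---|
| 3 v 10 | 0.067 | 0.092 |
| 3 v 11 | 0.046 | 0.057 |
| 3 v 12 | 0.032 | 0.035 |
| 0 v 6 | no finite OR | 0.031 |

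**The case against.** **The Apgar choice is a disclosed judgement.** A reader might infer that the SAP contradicts itself by adjusting for one post-dose newborn measure and refusing another. It does not. Read with section 8.2 (Infant carriage), its criterion is whether treatment may affect the variable, not timing alone. Carriage is a plausible direct target of an antibiotic, and the SAP judges Apgar and birthweight unlikely to be affected. A reader might also infer that the primary odds ratio is biased. Nothing in the SAP shows this, and if the judgement is right, the adjustment causes no bias. This objection stands. What remains is an assumption with no planned check on the primary result. Whether Apgar is tabulated by arm cannot be told, since section 7 says only "See dummy tables and consort diagram".

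**The intended model is clear enough.** Sections 6.3 and 6.6 both name country, and section 8.1 does not say that its list is complete. That makes the correction editorial, but it concerns the confirmatory test and should be settled before the code is broken.

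**The twin gap touches few mothers.** True; no harm is shown for mothers of singletons. One line closes it.

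**The sparse-data shortfall is conditional.** Also true. The culture-confirmed shares are assumptions, and at 20% the pooled model passes. The country analyses are exploratory. The 3 v 11 example was chosen: its neighbours fall on the same side of 0.05 by either test. The 0 v 6 case does not depend on that choice, because any outcome with no events in one arm gives no finite logistic odds ratio. The words *where possible* in section 6.3 leave room for discretion but set no threshold.

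**Sections 8 and 9 serve different reports.** This is the sensible reading of the two tests, but the SAP does not state it.

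**Conclusion.** The point holds as a set of inexpensive corrections that should be made. The firmest is the wording on country in the primary model. The adjustment for Apgar and birthweight is an untested assumption, and its effect cannot be sized from the SAP. The maternal models are undefined for mothers of twins.

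The sparse-data gap does not reach the primary outcome (about 72 events per parameter) or sepsis (about 56). It concerns secondary outcomes that could have fewer than 40 events and for which the SAP gives no rate, such as culture-confirmed sepsis, clinical malaria, mortality among very low birth weight infants and maternal death. These conclusions rest on the Table 6 incidences, full recruitment of 12,000 with no losses, and the SAP's own standard of 10 events per parameter. The culture-confirmed shares and the hypothetical event counts are illustrations only.

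**What to change.** 1. Add country to the primary model in section 8.1, so that it agrees with sections 6.3 and 6.6.
2. Prespecify a sensitivity analysis of the primary outcome with arm and country only, which is free of post-dose covariates. Because it also drops birthweight, it cannot isolate Apgar; if that is the aim, add a second model that drops Apgar alone.
3. Adjust maternal outcomes for country only, or state which twin's Apgar score and birthweight are used.
4. For every Primary-cohort secondary outcome with fewer than 10 events per parameter, use an unadjusted odds ratio with Fisher's exact test, and otherwise the adjusted model. The threshold is 40 events with arm, country, Apgar and birthweight, and 10 × 2 = 20 for a maternal model with arm and country. Do not carry over the literal 4%: it would send the primary outcome's components to Fisher's test as well.
5. For hospitalisation and maternal death, state that the section 8.1 result, under rule 4, is the one reported for the secondary endpoint and that the section 9 Fisher test is for the safety table only.

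The cost is SAP wording, one or two extra models and unadjusted results for the rarest outcomes.

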## 6.4 Missing Data

(ICH E3; 9.7.1, 11.4.2.2. ICH E9; 5.3. EMA Guideline on Missing Data in Confirmatory Clinical Trials)

### Primary cohort

Missing data will not be explicitly recorded for the outcomes in the Primary cohort because the outcomes that will be analysed in this cohort are measured through passive surveillance.

### Carriage and Anthropometric cohorts

Since outcomes are actively recorded in these cohorts, missing data may be recorded for some of the outcomes analysed in the Carriage and Anthropometric cohorts.

We anticipate some missing data at the 4-month time point because of the interruption due to the COVID-19 pandemic. Therefore, an available case analysis will be conducted in the Carriage cohort. The occurrence of missing data is unlikely to be associated with any particular characteristic of the women/neonates, and the risk of bias due to missing data is small.

The anthropometric cohort was recruited prior to the COVID-19 pandemic. Nevertheless, we expect some missing data due to loss to follow up, and will therefore conduct an available case analysis in this cohort. We will assess the risk of selection bias by comparing the baseline characteristics of children who are lost to follow up with those who remain in the cohort throughout follow up.

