#### Carriage cohort

The cohort will include all mother–newborn dyads/triads who meet the following criteria:

- Selected to be in the carriage cohort
- Included in the primary analysis cohort
- Contributed swabs at day 0 and day 6 (but not necessarily at day 28 or 4 months)
- All members of the dyad/triad alive and participating in the study at the time of the 4–month visit

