## **8.2 Carriage cohort**

### **Maternal carriage**

Maternal bacterial carriage will be analysed by estimating the proportion of women positive at day 6 and the proportion positive at one or more of the post-intervention time points (i.e. day 6, day 28 or 4 months). The latter will be estimated using women who have data available at all time points, i.e. women missing day 28 or 4-month data will be excluded from this analysis. However, a secondary analysis will be done using a multiply imputed dataset in which missing day 28 and 4-month carriage data are imputed using day 0 and day 6 data. For bacteria that are isolated from multiple sample types an individual will be identified as positive if bacteria are isolated from any of the samples (Table 5). For example,

women will be considered positive for *Klebsiella* at day 6 if bacteria are isolated from either the NPS or breast milk sample. Besides presenting the prevalence of individual bacteria, the bacteria will be grouped into gram positives (*S. pneumoniae*, *S. aureus*, GBS, GAS) and gram negatives (*E. coli*, *pseudomonas*, *Klebsiella*).

We will use logistic regression to compare the proportion positive by study arm adjusting for carriage at day 0. For example, *S. aureus* carriage on day 6 will be compared by calculating an odds ratio adjusted for *S. aureus* carriage on day 0. If the prevalence of a carriage outcome is <4% then an unadjusted odds ratio will be presented instead of the adjusted OR and Fisher's exact test will be used to calculate the p-value. The cut-off of 4% has been chosen to ensure that logistic regression is not used when there are fewer than 10 events per parameter as recommended by Peduzzi et al (1996).

A longitudinal analysis of carriage will be conducted using data from breast milk samples collected on day 6, day 28 and at 4 months. As with the other analyses, logistic regression will be used to adjust for carriage at day 0 where possible (i.e. provided the prevalence is  $\geq 4\%$ ). Two versions of the analysis will be done: the first will be restricted to women with complete data at all three time points, and the second will be done using the multiply imputed dataset. The prevalence at each time point and in each arm will be displayed graphically.

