### **Infant carriage**

With the exception of *Klebsiella*, which is tested for in NPS and RS, in samples collected from infants each bacteria is only tested for in one sample type (e.g. *S. pneumoniae* is tested for in NPS and *E.coli* is tested for in rectal swabs). Therefore, in contrast to the analysis of maternal carriage, there is no need to combine results across different sample types. Each bacteria will be compared between study arms at day 0, day 6, day 28 and 4 months (Table 4). Additionally, we will compare the proportion positive at any time point. We will use logistic regression to adjust for maternal carriage at day 0 if the prevalence is  $\geq 4\%$ , if the prevalence is less than this then we will calculate an unadjusted OR and use Fisher's exact test. Note that we have chosen to adjust for maternal carriage at day 0 rather than neonatal carriage because neonatal samples are collected after treatment and may, therefore, be affected by treatment. The prevalence at each time point and in each arm will be displayed graphically. As with the analysis of maternal carriage, the analyses will be

done in children with complete data and then repeated using multiply imputed data (missing day 28 and 4-month outcomes will be imputed from day 0 and day 6 outcomes).

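### Section 6.4 promises an available-case analysis of carriage, but Section 8.2 uses complete data for the breast-milk series and, on its natural reading, for the infant comparisons, and names no main version

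*SAP*

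**What the plan says.** Section 6.4 (Carriage and Anthropometric cohorts) gives the reason for its rule first: "We anticipate some missing data at the 4-month time point because of the interruption due to the COVID-19 pandemic". It then concludes that "an available case analysis will be conducted in the Carriage cohort". It gives no expected rate. Its only remark on imputation for this cohort concerns baseline covariates; multiple imputation of carriage outcomes is not mentioned.

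Section 6.2 (Carriage cohort) fits that rule. Entry requires swabs at day 0 and day 6, but not at day 28 or 4 months. All members of the dyad or triad must also be alive and participating at the 4-month visit.

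Section 8.2 sets out four kinds of analysis:

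- Maternal carriage at day 6: "Maternal bacterial carriage will be analysed by estimating the proportion of women positive at day 6". No complete-data condition is attached.
- Maternal carriage at any follow-up visit: "women missing day 28 or 4-month data will be excluded from this analysis", with a secondary analysis by multiple imputation.
- Longitudinal breast milk at day 6, day 28 and 4 months, in two versions: "the first will be restricted to women with complete data at all three time points", and the second uses the imputed data.
- Infant carriage, compared at each of four visits and also at any visit: the analyses are "done in children with complete data and then repeated using multiply imputed data". The same sentence likens this to the maternal analysis and says that missing day-28 and 4-month outcomes are to be imputed.

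**The concern.** For the breast-milk series, and probably for the infant comparisons, the two sections define different analysis sets for the same outcome. Take a child with swabs at day 0, day 6 and day 28 but none at 4 months. Under Section 6.4 that child counts in three comparisons. Under Section 8.2, if complete data means data at every visit, the child counts in none of the non-imputed comparisons.

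Two things follow. First, the SAP supports three candidate results for one outcome (available-case, complete-case and imputed) and does not name the main one for the infant and breast-milk analyses. That leaves room to choose once the results are known. Second, the complete-case version gives up precision at day 6 and day 28 because of gaps at a later visit, which is where the SAP itself expects them.

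**Working it through.** The SAP states no figure on this point, so there is none to reproduce. The conflict is one of text; the arithmetic only shows its possible size.

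**Step 1: compare the rules, outcome by outcome.**

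| Outcome | Section 6.4 | Section 8.2, non-imputed | Conflict? |
|---|---|---|---|
| Maternal, day 6 | available cases | whole cohort (day-6 swab is an entry condition) | no |
| Maternal, any follow-up visit | available cases | all visits required | no real conflict: the derived outcome needs all visits to be fully defined |
| Breast milk, each visit | available cases | all three visits required | yes, explicit |
| Infant, each visit | available cases | complete data, not defined | yes, on the natural reading |

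For infants, two features favour the all-visits reading: the sentence refers back to the maternal analysis, and its imputed counterpart fills in day 28 and 4 months.

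**Step 2: inputs for size.** N = 500 dyads (SAP Section 4.1). Let m be the share missing at 4 months. The SAP gives no value, so m is assumed, from 5% to 40%. Nothing is assumed missing at day 28, and prevalence and balance between arms are taken as unchanged.

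**Step 3: formulas.** Complete cases = 500 × (1 − m). Available cases at day 6 and day 28 = 500. Ratio of interval widths = √(500 / complete cases).

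| m | Complete cases | Observed samples dropped at day 6, and again at day 28 | Width ratio |
|---|---|---|---|
| 5% | 475 | 25 | √(500/475) = 1.03 |
| 10% | 450 | 50 | √(500/450) = 1.05 |
| 20% | 400 | 100 | √(500/400) = 1.12 |
| 30% | 350 | 150 | √(500/350) = 1.20 |
| 40% | 300 | 200 | √(500/300) = 1.29 |

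**Step 4: sensitivity to day-28 gaps.** If 10% are also missing at day 28, independently of 40% at 4 months, complete cases = 500 × 0.90 × 0.60 = 270. The ratio is √(500/270) = 1.36 at day 6 and √(450/270) = 1.29 at day 28. If instead everyone who missed day 28 also missed 4 months, complete cases = 500 × 0.60 = 300. The ratios are then 1.29 at day 6 and √(450/300) = 1.22 at day 28.

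**Step 5: a side effect.** Section 8.2 uses a 4% prevalence cut-off to secure at least 10 events per parameter. With two parameters (arm and day-0 carriage), 500 × 0.04 / 2 = 10, so the cut-off works only at about 500 subjects. With 400 it gives 400 × 0.04 / 2 = 8; with 300 it gives 6.

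**The case against.** A reader might infer that Section 8.2 restricts every carriage analysis to complete data. It does not. The maternal day-6 comparison carries no such condition, and for carriage at any visit it is reasonable to require all visits.

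A reader might also infer that the observed samples are lost altogether. They are not: each restricted analysis is repeated on imputed data, which keeps them. Both versions are pre-specified, which limits selective reporting but does not remove it while no main version is named.

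Nor is it certain that infants are dropped from every comparison. Complete data is not defined there. It could mean complete for the outcome being analysed, which would agree with Section 6.4. The all-visits reading is the more natural one, and the ambiguity needs settling either way.

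It would go too far to say that a fixed set of women has no merit. When prevalence is plotted over time, a constant set prevents changes in who was sampled from looking like changes in carriage. That supports keeping such a display, but not using it as the main comparison between arms at each visit.

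Finally, the size is uncertain. The SAP expects only some missing data. The cohort rule already removes dyads no longer participating at 4 months, so 500 is an upper bound and the remaining missingness may be modest. At 5% to 10% the widening is only 3% to 5%. Section 6.4 also considers missingness unlikely to depend on participant characteristics; on that premise the issue is precision, and the SAP gives no basis for claiming bias.

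**Conclusion.** The inconsistency holds in limited form. It is explicit for the breast-milk series and holds for the infant per-visit comparisons on the most natural reading of an undefined term. In those non-imputed versions, samples already collected are set aside because a later visit was missed, and no version is designated as the main one. The widening of day-6 and day-28 intervals is about 3% to 29% under the assumptions of 500 dyads, full day-28 data and 5% to 40% missing at 4 months. The text conflict stands whatever the rate. Only secondary carriage endpoints are affected; the primary endpoint is not. The change is worth making because it is cheap and follows the SAP's own stated rule.

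**What to change.** In Section 8.2, state that the main comparison at each time point, for infant swabs and for breast milk, uses all cohort members with a sample at that time point, as Section 6.4 says, and show the denominator for each. Keep the complete-data condition only for the outcomes of carriage at any time point, and state there that it means data at every relevant visit. Name multiple imputation as the sensitivity analysis in Section 8.2, and mention it in Section 6.4 so that the two sections agree. A complete-data version of the breast-milk graph may stay as a supplementary display.

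The cost is a wording change. The drawback is that denominators will differ between time points, so a trend across visits has to be read with that in mind.
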